10.2. Patient Disposition

All patient discontinuations will be documented, and the extent of each patient's participation in the study will be reported. If known, a reason for their discontinuation will be given.

10.3. Patient Characteristics

Patient characteristics will include a summary and/or listing of the following:

- Patient demographics including, for example, age, sex, ethnicity/race, weight, and screening body mass index (BMI) will be reported.
- Baseline disease characteristics
- Prior disease-related therapies
- Concomitant medications.

Other patient characteristics will be summarized as deemed appropriate.

10.4. Safety Analyses

All patients who receive at least 1 dose of either study drug will be evaluated for safety and toxicity. AE terms and severity grades will be assigned by the investigator using CTCAE, version 4.03).

Safety analyses will include summaries of the following:

- AEs, including severity and possible relationship to study drug, and concomitant medications
- dose adjustments
- laboratory values
- vital signs and physical examinations
- DLTs at each dose level
- ECGs

10.5. Pharmacokinetic Analyses

PK analyses will be conducted on patients who have received at least 1 dose of the study drugs and have had samples collected.

PK parameter estimates for LY2510924 will be calculated by standard noncompartmental methods of analysis. The primary parameters for analysis will be AUC of LY2510924. Other noncompartmental parameters, such as time of $t_{1/2}$, CL/F, and apparent volume of distribution (V/F) may be reported.

Summary statistics will be tabulated for the PK parameters of durvalumab.

Population PK analyses for LY2510924 and/or durvalumab may be conducted using a population PK approach. The relationship between LY2510924 and/or durvalumab exposure and selected safety outcomes, pharmacodynamics/biomarkers, and immunogenicity may be explored, if necessary.

10.6. Biomarker Analyses

Exploratory biomarkers will be summarized and assessed for correlations with clinical outcomes. Biomarker relationships by tumor type, changes in biomarker levels at baseline and over time, and differences among dose levels or exposure will be explored as possible.

The pharmacodynamic effect from all patients undergoing pharmacodynamic assessments will be explored.

10.7. Pharmacokinetic/Pharmacodynamic Analyses

PK/pharmacodynamic analyses for LY2510924 may be conducted as deemed necessary by Global PK/ pharmacodynamic management. These analyses may include, but are not limited to, establishing relationships (or lack of) between exposure and pharmacodynamic biomarkers that were explored or confirmed in pharmacodynamic analyses (refer to Section 10.6).

10.8. Immunogenicity

Immunogenicity incidence will be tabulated, and correlation to durvalumab, activity, and safety will be assessed, as appropriate, respectively. The measures that will be analyzed include baseline presence and level of ADA, treatment-emergent ADA, levels of neutralizing ADA, and incidence and levels of ADA related to IRRs.

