8.2.5. Samples for Immunogenicity Research

Blood samples for immunogenicity testing will be collected to determine ADA production against durvalumab. The specific time points are listed in [Attachment 4](#). Sample collection, storage, and shipment instructions for blood samples will also be provided in the Central Laboratory Manual. Pretreatment and post-treatment samples will be collected and assayed for

the presence of ADA using an immunoassay. The number and percentage of patients with positive antidrug response will be summarized. In the event of a study treatment-related infusion reaction, every effort should be made to collect blood samples for anti-durvalumab antibody determination, as well as blood samples for durvalumab serum concentration, as close to the onset of the reaction as possible, at the resolution of the event, and 30 days following the event.

Samples may be stored for a maximum of 15 years following last patient visit for the trial at a facility selected by the sponsor to enable further analysis of immune responses to study drugs. The duration allows the sponsor to respond to regulatory requests related to study drugs.

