Serum, Plasma, and Whole Blood Samples for Biomarkers		x	See Attachment 4 for exact timing.				x				Baseline sample for whole blood only, and must be collected ≤7 days prior to Cycle 1 Day 1. See Attachment 4 for exact timing.
Radiological Tumor Assessment	x				x		x				Local. CT scans will begin within 7 days prior to starting Cycle 3 and every other cycle afterwards including follow-up (approximately 8 weeks apart).

Relative Day Within a Cycle	Baseline		Cycle 1		Cycle 2	Cycle 3-n	Follow-Up				Comments
	<28 days	<7 days	1	15	1	1	30 day	60 day	90 day	LT FU ^a	
Visits							801	802	803	804	
Blood for pharmacogenetics		x									It is highly recommended to draw the whole blood sample on Cycle 1 Day 1 prior to the first dose; however, it can be collected later during the study if necessary.
Other safety or laboratory assessments; for example, immunogenicity					x	C4			x		Note: Day 1 sample should be taken prior to durvalumab and LY2510924.
Survival/ subsequent anticancer therapy							x	x	x	x	At long-term FUP, at least every 12 weeks ±7days until patient’s death or study completion.
Durvalumab			x		x	x					In clinic on Day 1 of each cycle.
LY2510924			Days 1-28		Days 1-28	Days 1-28					LY2510924 will be self-administered SQ daily. On Cycle 1 Days 1, 2, 15 and 16 and on Cycles 2 to 4 Day 1, LY2510924 should be taken at the clinic (time and date recorded) after a blood sample is taken for LY2510924 PK but prior to the start of durvalumab (refers to Day 1 of each cycle only).
Dispense study drugs and assess compliance			x		x	x					Collect drug diary prior to dispensing study drug for cycle.

Relative Day Within a Cycle	Baseline		Cycle 1		Cycle 2	Cycle 3-n	Follow-Up				Comments
	<28 days	<7 days	1	15	1	1	30 day	60 day	90 day	LT FU ^a	
Visits							801	802	803	804	
Dispense/ collect patient diaries			x		x	x					Patients will complete diaries once per cycle.

Abbreviations: aPTT = activated partial thromboplastin time; C = cycle; CEA = carcinoembryonic antigen; CT = computer tomography; CTCAE = Common Terminology Criteria for Adverse Events; D = day; ECG = electrocardiogram; ECOG = Eastern Cooperative Oncology Group; FUP = follow-up

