Pharmacokinetic (PK) samples will be collected for both LY2510924 and durvalumab and immunogenicity (IK) samples will be collected for durvalumab only. Predose sample for LY2510924 should be drawn as close as possible prior to the subcutaneous (SQ) injection of LY2510924, and that for durvalumab should be drawn as close as possible prior to start of durvalumab infusion (but can be drawn up to 1 hour or 60 minutes prior to the start of infusion). All post-dose blood draws for LY2510924 PK should be drawn in the preferred time windows listed in the table below. Exact clock reading for the time of blood draw should be recorded. While best effort should be done to draw the blood sample within the time window provided, it is more important to ensure that the predose sample for LY2510924 and durvalumab is actually collected before the administration of SQ injection and start of infusion, respectively, and post-end of infusion sample for durvalumab should be collected after the infusion has actually completed. It is also equally important to record actual date and time of blood collection for PK/IK sample on the Requisition Form after drawing the sample. Sample collection for PK/IK must be from the opposite arm to that used for study drug infusion. If drug was administered via a central venous catheter, the sample collection should be from a different site.

In addition, if a patient experiences an IRR, blood samples for anti-durvalumab antibody and PK should be drawn, with no more than 15 minutes' time difference between PK and IK samples. Samples will be taken at the following time points: (1) as soon as possible after the onset of the IRR, (2) at the resolution of the IRR, and (3) 30 days after the IRR.

Pharmacokinetic, Pharmacodynamic, and Biomarker Sampling Schedule

Cycle	Day	PK Sampling Time for LY25109 24 ^a	PK Sampling Time for Durvalumab	Durvalumab Immunogenicity	Blood for Pharmacogenetics	Tailoring and Pharmacodynamic Biomarker			
						Plasma for Exploratory Research	Serum for Exploratory Research	Whole Blood for Immunophenotyping Including CD34+ Counts ^c and Other Exploratory Research	Tissue for PD-L1 and Exploratory Research
—	≤7 days				X			X	
1	1	Predose ^b				X	X	X	X (Core or excisional biopsy of a tumor lesion or a recent biopsy defined by ≤3 years since last documented progression of disease)
1	1	0.5 hr +/- 15 min	10 min after end of infusion (+/-5 min)						
1	1	2 hr +/- 30 min						X	
1	1	4 hr +/- 30 min					X		
1	1	6 hr +/- 30 min							

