**Table CXAD.6.1. Data Handling Conventions**

Term	Definition or Rule
Relative Study Day	
If assessment is on or after date of first dose then  <math>(\text{date of assessment}) - (\text{date of first study drug dose}) + 1</math>
 
If assessment precedes first dose of drug then  <math>(\text{date of assessment}) - (\text{date of first study drug dose})</math>
 
There is no Study Day 0. Study Day 1 is the date of first dose and study day -1 is the day before the first dose.

Baseline	
For change from baseline analyses, baseline value is defined as the last reported measure on or before the first dose date (prior to the dose administration), unless otherwise specified.
 
For change from baseline within a cycle, baseline value is defined as the measure prior to the first dose of that cycle, unless otherwise specified.
 
If more than one pre-dose measure is available, they may be averaged if appropriate.

Entered	Patients who have signed the informed consent form directly or through their legally acceptable representatives.
Enrolled	Patients who have been assigned to a study treatment and have received at least one dose of study treatment.

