### **6.12. Immunogenicity Analyses**

Immunogenicity incidence will be tabulated, and correlation to MEDI4736, activity, and safety will be assessed, as appropriate, respectively. The measures that will be analyzed include baseline presence and level of ADA, treatment-emergent ADA, levels of neutralizing ADA, and incidence and levels of ADA related to IRRs.

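### Section 8.2.5 promises pretreatment ADA samples, but both sampling schedules start ADA collection at Cycle 2 Day 1, so baseline ADA cannot be analysed from the samples as scheduled

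*Protocol*

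**What the plan says.** Protocol Section 5.4.2 makes characterising the immunogenicity of durvalumab, given with LY2510924, a secondary objective. For the analysis, Protocol Section 10.8 states: "The measures that will be analyzed include baseline presence and level of ADA, treatment-emergent ADA, levels of neutralizing ADA". SAP Section 6.12 carries the same list: "The measures that will be analyzed include baseline presence and level of ADA, treatment-emergent ADA".

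On sampling, Protocol Section 8.2.5 states "Pretreatment and post-treatment samples will be collected and assayed for" the presence of ADA, and on timing "The specific time points are listed in" Attachment 4. The introduction to Attachment 4 adds that "immunogenicity (IK) samples will be collected for durvalumab only". The matching row of the Study Schedule in Attachment 1 is labelled "Other safety or laboratory assessments; for example, immunogenicity".

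Both documents also provide for extra ADA samples when an infusion-related reaction occurs. Attachment 4 times these "1) as soon as possible after the onset of the IRR, (2) at the resolution of the IRR", with a third 30 days later.

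SAP Table CXAD.6.1 gives the general convention: "baseline value is defined as the last reported measure on or before the first dose date (prior to the dose administration").

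**The concern.** The analysis sections and Section 8.2.5 assume a pretreatment ADA sample. The two tables that sites will work from do not contain one. A site following the tables draws no baseline sample; a site following the text of Section 8.2.5 may draw one.

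Two of the named measures are affected. Baseline presence and level of ADA have no scheduled data at all. Treatment-emergent ADA is compromised because a first positive result at Cycle 2 Day 1 cannot be separated from reactivity that was there before treatment. Within the scheduled samples, only seroconversion after a negative day-29 result can be identified. Once a patient has been dosed, a dedicated predose sample can no longer be obtained, and both documents say that missing data of this kind will not be imputed.

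**Working it through.** The plan gives no figure to reproduce here. The check is to read each immunogenicity cell in the two schedules and count the samples before the first durvalumab dose, which Protocol Section 7.2.1.2 places on Cycle 1 Day 1.

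| Time | Attachment 4, durvalumab immunogenicity column | Attachment 1, immunogenicity row |
|---|---|---|
| Baseline, within 7 days | Empty (marks under pharmacogenetics and whole blood) | Empty |
| Cycle 1 Day 1, predose | Empty (LY2510924 PK sample; marks under plasma, serum, whole blood, tissue) | Empty |
| Rest of Cycle 1 | Empty | Empty |
| Cycle 2 Day 1 | Marked | Marked |
| Cycle 4 Day 1 | Marked | Marked (C4) |
| 90 days after treatment | Marked | Marked |

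**Count.** Scheduled ADA samples before the first dose: 0 in Attachment 4 and 0 in Attachment 1. Scheduled ADA samples in total: 3, all after the first dose.

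**Timing with 28-day cycles.**
- Cycle 2 Day 1 is nominal day 1 + 28 = 29.
- Cycle 4 Day 1 is nominal day 1 + 3 × 28 = 85.

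**Reaction-triggered samples.** These are taken at onset, at resolution and 30 days later. All follow the start of an infusion, so none is a predose value under SAP Table CXAD.6.1.

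**Rate of pre-existing reactivity.** The documents give none. Their one ADA figure (Protocol Section 5.5.2.4) is 8 positive of 388 patients with samples: 8/388 = 2.1%, exact (Clopper-Pearson) 95% CI 0.9% to 4.0%. It is not split into pre-existing and treatment-emergent.

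**Illustration only.** With an assumed pre-existing rate p and n = 45, the expected number of such patients is 45p and the chance of at least one is 1 − (1 − p)^45.

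| Assumed p | Expected patients | Chance of at least one |
|---|---|---|
| 1% | 45 × 0.01 = 0.45 | 1 − 0.99^45 = 36% |
| 2% | 45 × 0.02 = 0.90 | 1 − 0.98^45 = 60% |
| 5% | 45 × 0.05 = 2.25 | 1 − 0.95^45 = 90% |

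**The case against.** The contradiction between Section 8.2.5 and Attachment 4 is hard to dispute. The arguments on the other side concern how much it matters.

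- **The sample is already required.** Section 8.2.5 promises it, so this could be seen as an omitted tick. But that section sends the reader to Attachment 4 for the times, and Attachment 4 has none before Cycle 2. Amendment (b) corrected the 90-day entry in this same column and left the gap.
- **The Attachment 1 comment.** It asks for the Day 1 sample to be drawn before both drugs. The Day 1 visits marked in that row are Cycles 2 and 4, so the comment sets the time within those visits and adds no Cycle 1 sample. The row is a catch-all, which makes it weaker corroboration, but it agrees with Attachment 4.
- **Reaction-triggered samples.** After a reaction to the first infusion, an early negative followed by a positive would show seroconversion by day 29. This is true for such patients. It is why the statement about seroconversion is limited to scheduled samples, and it still supplies no baseline.
- **Stored serum.** Cycle 1 Day 1 predose serum is scheduled, and Section 8.2.3.1 allows storage for up to 15 years. Retrospective testing might recover a baseline. The documents do not assign this serum to the ADA assay, so recovery is possible but unplanned.
- **The illustration.** The 5% assumption lies above the upper confidence limit for all ADA positivity in the one study cited. That is fair. If all 8 positives there had been pre-existing, the expected number here would be 45 × 8/388 = 0.9. The finding rests on the absence of scheduled samples and does not depend on these rates.
- **The SAP definition.** The Table CXAD.6.1 convention is introduced for change-from-baseline analyses and allows exceptions, and SAP Section 6.12 gives no rule for treatment-emergent ADA. Both points are correct, but neither removes the need for a predose sample.

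**Conclusion.** The concern holds. As scheduled, 0 of about 45 patients have an ADA baseline, and the first scheduled result comes 28 days after the first durvalumab dose. Baseline presence and level of ADA cannot be reported from those samples, and a positive result on day 29 cannot be classified.

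The number of patients who would be misclassified or unclassifiable is unknown. On the one ADA rate in the documents it is likely to be small: about one patient even if all earlier positives had been pre-existing. The count assumes sites follow the schedules and the exploratory serum is not redirected to the ADA assay.

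The analyses are descriptive, and no primary endpoint or dose decision uses ADA. The defect therefore limits one secondary objective and should be fixed.

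**What to change.** Add a durvalumab immunogenicity mark in the Cycle 1 Day 1 predose row of Attachment 4 and under Cycle 1 Day 1 in the immunogenicity row of Attachment 1, before either drug is given. The schedules then match Section 8.2.5. The predose convention in SAP Table CXAD.6.1 can be applied to the new sample, so closing this gap requires no change to SAP Section 6.12.

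The cost is about one extra tube at a draw where PK, plasma, serum and whole blood are already taken, with no new visit or procedure.

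The alternative is to delete baseline and treatment-emergent ADA from Protocol Section 10.8 and SAP Section 6.12 and correct Section 8.2.5. That would also make the text consistent, but it gives up part of a secondary objective to save one tube.

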10.9. Efficacy

Tumor response data will be provided by cohort/expansion arm (according to RECIST v1.1). Particularly, the antitumor effect will be summarized by best overall response, including the overall response rate (ORR) and disease control rate (DCR). A patient is considered to have a tumor response if they achieve a confirmed CR or PR. The ORR will be estimated by dividing the total number of confirmed complete and partial responders (CR+PR) by the total number of enrolled patients. The DCR will be estimated by dividing the total number of CR+PR+SD by the total number of enrolled patients. A 95% exact CI will be constructed to determine the level of precision of the ORR and DCR. Time-to-event variables such as PFS, time to response, duration of response and overall survival will be tabulated, and the Kaplan-Meier method (Kaplan and Meier 1958) will be used to estimate the survival curves, medians, and survival rates (eg, 6-month survival rate) if applicable.

10.10. Interim Analyses

Data will be reviewed on a cohort-by-cohort basis during Phase 1a of the study, until the MTD is determined. The purpose of these cohort-by-cohort reviews is to evaluate the cumulative safety data (Cycle 1 and all later cycles) at each dose level(s) that has/have enrolled study patients, and

determine if a DLT has been observed that would suggest MTD has been met or exceeded. The investigators and the Lilly study team in consultation with collaborator will make the determination regarding dose escalation based upon their review of the safety and tolerability data as described in this protocol.

Safety and/or PK data will be reviewed during the study if needed for dose escalation, modifications to the dose-escalation strategy or other design elements.

Once MTD is determined for Phase 1a, an interim analysis will be performed prior to opening Phase 1b.

In Phase 1b, if a DLT-equivalent toxicity occurs in one-third or more of patients during Cycle 1 (with a minimum of 6 patients enrolled), a data review will be performed to determine whether to continue at the current LY2510924 dose or whether the dose of LY2510924 should be reduced. If the DLT-observation period is extended to 2 cycles during Phase 1a, this analysis will also include DLT-equivalent toxicities occurring in Cycle 2.

In Phase 1b, a safety review may occur for each expansion arm approximately 2 months after approximately 8 of the planned patients per arm start study therapy.

If an unplanned interim analysis is deemed necessary, the sponsor will determine if it is necessary to amend the protocol.

Any interim analyses may be combined if they are expected to occur within approximately a month, and interim analyses may also be combined with the ongoing trial-level safety review or annual safety review for annual safety update reporting.

The final analysis and evaluation of the primary objective and the secondary objectives will be performed no more than 12 months after the last patient of each expansion arm starts study therapy, and the final analysis may be conducted separately for each expansion arm. A clinical study report might be created before the last patient visit. In this case, all data until the data-cutoff date will be used for the analysis of safety, efficacy, PK, and pharmacodynamic biomarkers.

11. Informed Consent, Ethical Review, and Regulatory Considerations

11.1. Informed Consent

The investigator is responsible for ensuring that the patient understands the potential risks and benefits of participating in the study, including answering any questions the patient may have throughout the study and sharing in a timely manner any new information that may be relevant to the patient's willingness to continue his or her participation in the study in a timely manner.

The ICF will be used to explain the potential risks and benefits of study participation to the patient in simple terms before the patient is entered into the study and to document that the patient is satisfied with his or her understanding of the potential risks and benefits of participating in the study and desires to participate in the study.

The investigator is ultimately responsible for ensuring that informed consent is given by each patient or legal representative before the study is started. This includes obtaining the appropriate signatures and dates on the ICF prior to the performance of any protocol procedures and prior to the administration of study drug.

Lilly or its representatives must approve all ICFs before they are used at investigative sites(s). All ICFs must be compliant with the ICH guideline on GCP.

11.2. Ethical Review

The sponsor or its representatives must approve all ICFs before they are used at investigative sites. All ICFs must be compliant with the ICH guideline on GCP.

Documentation of ERB approval of the protocol and the ICF must be provided to Lilly before the study may begin at the investigative site(s). The ERB(s) will review the protocol as required.

Additionally, the study site's ERB(s) should be provided with the following:

- the current IB and updates during the course of the study
- ICF
- relevant curricula vitae

11.3. Regulatory Considerations

This study will be conducted in accordance with:

- 1) consensus ethics principles derived from international ethics guidelines, including the Declaration of Helsinki and Council for International Organizations of Medical Sciences (CIOMS) International Ethical Guidelines
- 2) the ICH GCP Guideline [E6]
- 3) applicable laws and regulations.

The investigator or designee will promptly submit the protocol to applicable ERB(s).

Some of the obligations of the sponsor will be assigned to a TPO.

An identification code assigned to each patient will be used in lieu of the patient's name to protect the patient's identity when reporting AEs and/or other study-related data.

